6. STUDY ACTIVITIES

6.1 SCREENING PERIOD

The screening period is the time period up to 48 hours before enrollment when a patient is identified, informed consent is obtained, and the patient is evaluated for inclusion in the clinical trial. Parental permission will be obtained from parents and/or legally authorized representatives (LAR) on a written informed consent document. Because of the critically ill nature of the study population, it is expected that most children will not be able to provide assent. Only adverse events directly related to the screening procedures will be reported during this time.

Medical history and test results must be examined to ensure the patient meets all eligibility criteria. Tests that are specific to this protocol (i.e. not standard of care) require the patient or legal representative to have provided written consent for participation.

Any patients that do not meet study criteria, will not be enrolled into the study. These patients will not be counted in the overall study enrollment numbers, but will be listed on the screening log.

Prior to enrollment please contact the study sponsor or designee below to validate that the patient has met all inclusion and exclusion criteria.

[name] [REDACTED]
University of Michigan
Internal Medicine-Nephrology
[name]
[name]

OR

[name] MD [REDACTED]

Cincinnati Children's Hospital Medical Center (CCHMC)
[name]
[name]

6.2 CRRT PARAMETERS

6.2.1 CITRATE ANTICOAGULATION

Each participating clinical site will use their regional citrate anticoagulation protocol. The clinical site is responsible to achieve and maintain a serum post filter ionized calcium level of <0.40 mmol/L throughout the entire SCD treatment period (day and night). The serum post filter ionized calcium level will be collected from the CRRT Circuit post SCD [REDACTED]. Examples of regional citrate anticoagulation protocols are included in Appendix D. If the site has difficulty in maintaining post-fiter iCa levels <0.4 mM from prior experience with patients in this body weight between 10 and 20 kg body weight, the Sponsor and Lead Investigator will discuss options of citrate protocols to be used in enrolled patients to meet post filter iCa levels <0.4 mM as required during SCD treatment.

See the RCA example protocol in Appendix D.

Clinical sites will utilize the following parameters to alleviate the metabolic derangements associated with regional citrate based anticoagulation:

- a) *Alkalosis:* Patients with an arterial pH <7.40 at enrollment will initiate CRRT with solutions containing either 25 or 35 meq/L of base as directed by local standard of care. During the study, if the patient's arterial pH increases to >7.45 OR the patient's serum bicarbonate increases to >35 meq/L, the CRRT solution will be changed to a base concentration of 25 meq/L, OR 0.9% NaCl will be added dialysis fluid to correct the alkalosis per local standard of care.
- b) *Citrate lock:* If the patient develops citrate lock, as defined by a serum ionCa <0.95 mmol/L and a total serum Ca >12.5 meq/L, the citrate infusion will be discontinued OR the CRRT clearance will be increased by 50% or per local standard of care, AND CRRT circuit Ca and patient Ca will be checked at least every one hour. For centers that stop citrate, once the patient ionCa is >1.0 mmol/L, the citrate will be restarted at a lower rate determined by the site investigator, and hourly ionCa pairs will be rechecked x 3 to ensure a stable patient ionCa >1 mmol/L and stable circuit ionCa <0.40 mmol/L.

Of importance the clinical plan is to monitor the perfusion circuit iCa levels at least q1h \pm 30min at the initiation of regional citrate anticoagulation (RCA) until a steady state iCa range is between 0.25 to 0.40 mmol/L. Once established, iCa levels both in the circuit and in the patient will be monitored q6h \pm 1hr. If the iCa is outside the targeted range or alterations in citrate or calcium infusion rates are made, iCa levels are measured at least q1h \pm 30min until targeted ranges are once again achieved. Of importance, for efficacy of SCD treatment, iCa levels must be maintained in the recommended range at least 90% of the time, based on a sensitivity analysis showing that the mortality endpoint difference was lower with target iCa 80-85% of total treatment in clinical trial SCD-003.

The protocol example identified in **Appendix D** may be utilized.

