7. TREATMENT INTERRUPTIONS – DISCONTINUATION CRITERIA

7.1. TREATMENT DISCONTINUATION CRITERIA

Subjects may be withdrawn from therapy prior to hour 240 for a variety of reasons. When therapy is discontinued prior to hour 240, the follow-up period will immediately begin and data will continue to be collected per protocol.

The Principal Investigator will assign a primary reason for therapy termination utilizing the categories listed in 7.2 and 7.3 below, and if appropriate, one or more subcategories. The Principal Investigator will notify the Sponsor or designee within 24 hours of withdrawal of participation.

7.2. CLINICAL CRITERIA:

1. Improvement in Clinical Status

If a subject's condition improves (e.g. renal condition has improved to the extent that CRRT can be discontinued or hemodynamic status has improved so that the dialysis modality can be changed from CRRT to IHD) treatment may be discontinued before the 240 hour treatment period. The decision to discontinue treatment based upon improvement in clinical status will be made by the Principal Investigator.

2. CRRT related events

Such as inability to maintain vascular access based upon PI's clinical assessment. Includes failure of the CRRT device and/or circuit that requires treatment to be discontinued prior to hour 240 of therapy.

3. SCD related medical events

Such as persistent leukopenia, neutropenia or thrombocytopenia based upon PI's clinical assessment of relationship to SCD.

4. SCD Failure/Malfunction

Any failure of the SCD that requires treatment to be discontinued prior to hour 240 of therapy e.g. clotting or evidence of leakage in the SCD or inability to maintain a patent circuit.

5. Death or withdrawal of life support**6. Regional Citrate Anticoagulation Intolerance**

All subjects must be able to tolerate and achieve satisfactory regional citrate anticoagulation. Tolerance of regional citrate anticoagulation is defined as achieving:

- Two (2) consecutive circuit ionized calcium levels of < 0.40 mmol/L (or < 1.6 mg/dL),
- At least 30 minutes apart, and
- Within the first 12 hours of SCD initiation.

If unable to achieve the specific circuit ionized calcium levels within the time frame above, treatment with the SCD must be discontinued. The subject will progress on to the post-SCD follow up period, unless the subject and/or legal guardian withdraws consent for the study.

7. Hematologic Events

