APPENDIX D –REGIONAL CITRATE ANTICOAGULATION (RCA) PROTOCOL EXAMPLE

1. **Purpose:** The purpose of the guidelines is to standardize, to the extent possible, the provision of regional citrate anticoagulation to patients who require CRRT. While these guidelines should govern the CRRT prescription provided to most patients, there will be special circumstances (e.g. inborn errors of metabolism, exogenous toxin removal) that will require deviation from these guidelines.
2. **Regional citrate anticoagulation:** All CRRT circuits will receive regional citrate anticoagulation. The initial prescription and calcium level monitoring will be based on the size of patients and the presence, or lack thereof, of significant hepatic dysfunction. **REMEMBER TO ACCOUNT FOR THESE FLUIDS IN THE PATIENT REMOVAL RATE AS THESE ARE EXTERNAL TO THE CRRT MACHINE.**
 - a. **Patients > 1 year of age and with normal hepatic function:**
 - i. Order ACD-A™ and CaCl₂ (8 grams/1 liter NS) to bedside
 - ii. Initial ACD-A™ rate = 1.5 x CRRT blood pump rate x min/hour (e.g., if blood pump rate is 100 ml/minute; the ACD-A™ rate is 150 ml/hour). This is to be infused at a stopcock or y-connector on access line.
 - iii. Initial CaCl₂ rate = 0.6 x blood pump rate x min/hour (e.g., if blood pump rate is 100 ml/minute; the CaCl₂ rate is 60 ml/hour).
 - iv. Calcium monitoring schedule
 1. Check patient total and ionized calcium prior to CRRT initiation.
 2. Check patient and system ionized calcium 5 minutes after CRRT settings at prescribed rates.
 3. Check patient and system ionized calcium 1 hours after CRRT settings at prescribed rates.
 4. Check patient and system ionized calcium every 6 hours thereafter
 5. Check patient total calcium daily
 6. Check patient and system ionized calcium one hour after any change in ACD-A™ or CaCl₂ rate
 - b. **Desired Calcium Concentration ranges**
 - i. Circuit ionized calcium = 0.25 to <0.40 mmol/L
 - ii. Patient ionized calcium = 1.1 to 1.3 mmol/L (a higher level may be requested by ICU/CICU service if clinically indicated)
 - iii. Patient systemic calcium = 8 to 12 mg/dL
 - c. **Citrate anticoagulation management**

- i. Bedside RN to call for patient ionCa < 1 mmol/L or >1.5 mmol/L, or circuit ionCa < 0.25 mmol/L or \geq 0.40 mmol/L
- ii. Circuit ionCa managed with ACD-A™ rate
 1. For circuit ionCa < 0.25 mmol/L, decrease ACD-A™ 10%
 2. For circuit ionCa \geq 0.40 mmol/L, increase ACD-A™ 10%
- iii. Patient ionCa managed by CaCl₂ rate

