8-8.9 g/dL	0.86	0.9	0.93	0.97	1	1.04	1.07	1.11	1.14	1.18	1.21
9-9.9 g/dL	0.83	0.86	0.89	0.93	0.96	1	1.03	1.07	1.1	1.13	1.17

10-10.9 g/dL	0.79	0.82	0.86	0.89	0.92	0.96	0.99	1.02	1.05	1.09	1.12
11-11.9 g/dL	0.75	0.78	0.82	0.85	0.88	0.91	0.94	0.98	1.01	1.04	1.07
12-12.9 g/dL	0.73	0.76	0.79	0.82	0.85	0.88	0.91	0.94	0.97	1	1.03
13-13.9 g/dL	0.69	0.72	0.75	0.78	0.8	0.83	0.86	0.89	0.92	0.95	0.98
14-14.9 g/dL	0.65	0.68	0.71	0.73	0.76	0.79	0.82	0.84	0.87	0.9	0.93
15-15.9 g/dL	0.61	0.64	0.66	0.69	0.72	0.74	0.77	0.8	0.82	0.85	0.88
16-16.9 g/dL	0.57	0.6	0.62	0.65	0.67	0.7	0.72	0.75	0.78	0.8	0.83
17-17.9 g/dL	0.53	0.56	0.58	0.61	0.63	0.65	0.68	0.7	0.73	0.75	0.78
18-18.9 g/dL	0.5	0.52	0.54	0.57	0.59	0.61	0.63	0.66	0.68	0.7	0.73
19-19.9 g/dL	0.46	0.48	0.5	0.53	0.55	0.57	0.59	0.61	0.63	0.65	0.68

Adjust the Ca-infusion rate +/-10-20% using systemic iCa levels every 6 hours:

It is expected that the systemic iCa will usually be near GOAL +/-0.1 mM with the initial Ca infusion rate. Some patients may sequester Ca in their tissues (for instance with acute pancreatitis or rhabdomyolysis) or conversely may release Ca from their bones (for instance with hypercalcemia of malignancy). Systemic citrate accumulation to maximum 1.5-2 mM is also possible in severe shock/liver failure. Such patients may require +10-20% adjustments to their initial Ca-infusion rate based on systemic iCa levels as in Table 3. Systemic iCa >1 mM will be achieved with total Ca \leq 12 mg/dL with the above settings even in severe liver failure.

Table 3: 81.6 mM CaCl₂ Infusion Rate Change Based on Systemic iCa Every 6 hours:

	The patient's ionized calcium level checked every 6 hours: GOAL 1.15 mM				
	Less than <0.95 mmol/L	0.95 – 1.04 mmol/L	1.05 - 1.25 mmol/L	1.26 – 1.4 mmol/L	More than >1.4 mmol/L
Current Ca-infusion Flow Rate mL/h	Increase Rate +20%; notify ICU physician	Increase Rate +10%	No Change	Reduce Rate -10%	Reduce Rate -20%; notify ICU physician
<12	+2 ml/h	+1 ml/h	No change	-1 ml/h	-2 ml/h
12-<17	+3 ml/h	+1.5 ml/h	No change	-1.5 ml/h	-3 ml/h
17-<22	+4 ml/h	+2 ml/h	No change	-2 ml/h	-4 ml/h
22-<27	+5 ml/h	+2.5 ml/h	No change	-2.5 ml/h	-5 ml/h
27-<32	+6 ml/h	+3 ml/h	No change	-3 ml/h	-6 ml/h
32-<37	+7 ml/h	+3.5 ml/h	No change	-3.5 ml/h	-7 ml/h
37-<42	+8 ml/h	+4 ml/h	No change	-4 ml/h	-8 ml/h
42-<47	+9 ml/h	+4.5 ml/h	No change	-4.5 ml/h	-9 ml/h

47-<52	+10 ml/h	+5 ml/h	No change	-5 ml/h	-10 ml/h
52-<57	+11 ml/h	+5.5 ml/h	No change	-5.5 ml/h	-11 ml/h

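### The citrate-lock trigger in Section 6.2.1(b) gives total serum calcium in meq/L; as written it equals 25 mg/dL, about twice the 12 mg/dL limit in Appendix D, and mg/dL was probably meant

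*Combined protocol and SAP*

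**What the plan says.** Section 6.2.1 lets each site use its own regional citrate protocol, then sets two management rules for all of them: "Clinical sites will utilize the following parameters to alleviate the metabolic derangements associated with regional citrate based anticoagulation". Item (a) covers alkalosis and uses meq/L for base and bicarbonate, for example "serum bicarbonate increases to >35 meq/L". Item (b) covers citrate lock, "as defined by a serum ionCa <0.95 mmol/L and a total serum Ca >12.5 meq/L". When that definition is met, the site must stop citrate or increase CRRT clearance by 50% (or follow local standard of care), and check circuit and patient calcium at least hourly.

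Elsewhere the protocol handles calcium as follows:

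- Section 7.2, item 6 (circuit ionized calcium): "Two (2) consecutive circuit ionized calcium levels of < 0.40 mmol/L (or < 1.6 mg/dL").
- Appendix D, item 2.b (target for total calcium): "Patient systemic calcium = 8 to 12 mg/dL".
- Appendix D, item 2.a.iv (the measurement that would be compared with the threshold): "Check patient total calcium daily".
- Appendix D, fixed-flow settings: "Systemic iCa >1 mM will be achieved with total Ca" at or below 12 mg/dL.
- Appendix A, PRISM II table: calcium in mg/dL, with potassium and bicarbonate in mEq/L.

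**The concern.** The number 12.5 sits naturally beside a 12 mg/dL upper limit, but the unit attached to it is meq/L, which for calcium gives a much higher concentration. The two conditions are joined by *and*, so an unreachable or very high total-calcium threshold disables the whole definition, however low the ionized calcium falls.

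What is at stake is a safety step in critically ill children of 10 to 20 kg. Item 6.2.1(b) is the only text that links low patient ionized calcium to stopping citrate or raising clearance. In Appendix D the citrate rate is adjusted on circuit ionized calcium, and the written response to low patient ionized calcium is to infuse more calcium. The protocol itself expects that citrate can accumulate in severe shock or liver failure (Appendix D, fixed-flow settings). Enrolment requires non-renal organ failure or sepsis, and liver dysfunction is not a listed exclusion.

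**Working it through.** **Inputs**

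- Threshold as written: 12.5 meq/L (Section 6.2.1(b)).
- Appendix D upper limit for total calcium: 12 mg/dL.
- Protocol conversion: 0.40 mmol/L = 1.6 mg/dL (Section 7.2, item 6).
- Valence of calcium: 2, so mmol/L = meq/L ÷ 2.

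**Step 1. Reproduce the protocol's conversion.** With a molar mass of 40.078 g/mol, 0.40 × 40.078 ÷ 10 = 1.603 mg/dL, which agrees with the stated 1.6. The protocol's rounded factor is 1.6 ÷ 0.40 = 4 mg/dL per mmol/L.

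**Step 2. Convert the threshold as written.**

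- 12.5 ÷ 2 = 6.25 mmol/L
- 6.25 × 4 = 25.0 mg/dL (25.05 with the exact molar mass)
- 25.0 ÷ 12 = 2.08, and 25.0 − 12 = 13 mg/dL above the Appendix D limit

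**Step 3. Convert it as if the unit were mg/dL.**

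- 12.5 ÷ 4 = 3.125 mmol/L
- 12.5 ÷ 12 = 1.04, and 12.5 − 12 = 0.5 mg/dL above the limit

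| Reading | mmol/L | mg/dL | Ratio to 12 mg/dL | Total ÷ ionized at ionCa 0.95 mmol/L |
|---|---|---|---|---|
| As written (meq/L) | 6.25 | 25.0 | 2.08 | 6.6 |
| As mg/dL | 3.125 | 12.5 | 1.04 | 3.3 |

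For comparison, the largest total-to-ionized ratio that fits inside Appendix D's desired ranges (total 12 mg/dL = 12 ÷ 4 = 3.0 mmol/L, ionized 1.1 mmol/L) is 3.0 ÷ 1.1 = 2.7. The mg/dL reading lies a little above that ratio; the written reading is more than double it.

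**Step 4. Where the two readings part.** They differ when ionized calcium is below 0.95 mmol/L and total calcium is above 12.5 and up to 25 mg/dL (above 3.125 and up to 6.25 mmol/L). As a hypothetical case, take ionized calcium 0.90 mmol/L and total calcium 15 mg/dL, which is 15 ÷ 4 = 3.75 mmol/L. This is below 6.25, so not citrate lock as written; it is above 3.125, so citrate lock in mg/dL.

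**Step 5. Frequency.** The documents give no distribution of total calcium, so the number of children in that zone cannot be estimated.

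**The case against.** The strongest reply is that little turns on this in practice. Sites follow their own citrate protocols. The written threshold says when action is required, not when it is allowed, and Section 7.2, item 8 lets the investigator end SCD treatment for any documented reason. Alerting does not depend on the unit where Appendix D is followed: "Bedside RN to call for patient ionCa < 1 mmol/L or >1.5 mmol/L", and its Table 3 has the ICU physician told at ionized calcium below 0.95 mmol/L, the same ionized cut-off as in the citrate-lock definition. Section 6.2.1 also calls for ionized calcium at least hourly when it is out of range. Under the fixed-flow settings, total calcium is expected not to exceed 12 mg/dL, where neither reading would fire. Enrolment is at most 10 children, and experienced staff may read the figure as mg/dL anyway.

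Most of this stands as a limit on the likely harm; it does not cure the text. The reference to local standard of care in item (b) qualifies the action, not the definition. Appendix D is an example protocol, and the step attached to its Table 3 notification is a calcium increase, not a halt to citrate. Nothing in the documents tells staff to read 12.5 as mg/dL.

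Two further objections are fair. A complication trigger should lie above a target range, so the ratio of 2.08 is not itself the measure of the error; the better evidence is the factor of two between the two readings together with the use of mg/dL for total calcium elsewhere. And this is a unit inconsistency, not a failed calculation.

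**Conclusion.** The threshold is wrong as written. The inconsistency of the unit is certain: 12.5 meq/L of calcium is 25 mg/dL, 13 mg/dL above Appendix D's upper limit, and no other sentence states calcium in meq/L. That mg/dL was intended is a strong inference, not a stated fact. It rests on 12.5 mg/dL falling 0.5 mg/dL above the 12 mg/dL limit, on mg/dL being the unit for every other total-calcium figure that carries one, and on the repeated use of meq/L in the item just before, from which the label may have been carried over.

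The consequence is confined to safety management: the required stop-citrate or raise-clearance step is not triggered for total calcium above 12.5 and up to 25 mg/dL. Its frequency is unknown. No endpoint, estimate or analysis is affected. It should be fixed because it is a mandatory trigger for all sites, and its correct working should not depend on staff silently correcting the unit.

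**What to change.** Ask the clinical lead to confirm the intended value. If it is mg/dL, amend Section 6.2.1(b) so that citrate lock is ionized calcium below 0.95 mmol/L together with total serum calcium above 12.5 mg/dL (about 3.1 mmol/L), and notify sites. If another value was meant, state it in mg/dL so that it can be set directly against the 8 to 12 mg/dL range in Appendix D; if 12.5 meq/L was truly intended, give it as 25 mg/dL and justify it.

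The cost is one corrected unit and a note to sites. Design, endpoints and sample size are unaffected.

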6.2.2 BLOOD CIRCUIT VOLUME

The additional blood volume for the SCD is 120 ml. This additional circuit blood volume for the standard SCD in enrolled patients can be handled with blood priming with matched blood similar to the standard practice in neonates. Blood prime will occur if the total extracorporeal circuit volume (ECV) is greater than 10% of the patient's blood volume, based on an estimate of blood volume = 70 ml/kg x patient body weight (kg) [25]. The situation is most commonly encountered in neonatal CRRT, where circuit ECV can represent nearly 50% of patient blood volume, yet the same principles apply for this clinical study. [26]

Hypotension associated with blood priming can occur from transient dilution of vasoactive medications (e.g., norepinephrine), or from exposure to the hyperkalemic, hypocalcemic acidotic nature of blood banked blood, which can cause a bradykinin release syndrome (BRS) when the blood is exposed to the CRRT membrane. The BRS is usually associated with AN-69 membranes that will not be used in this study. Each center has its own blood priming protocol to mitigate the potential for this reaction. However, minimum standards for blood priming in this trial are detailed in **Appendix E** to ensure patient safety. [27]

Patients with AKI requiring CRRT are often hypotensive prior to initiation of CRRT. Initiation of CRRT itself can improve hemodynamics by correcting acidosis and hypocalcemia. Most patients with hemodynamic instability receive vasoactive medications. Since the age range and associated normal blood pressure parameters is wide for this pediatric study, it is difficult to

mandate an age specific lower blood pressure threshold to preclude CRRT initiation, especially if CRRT can address the instability as noted above. However, a threshold BP of 80/40 mmHg-- patients with both a systolic blood pressure of less than 80 mmHg and a diastolic blood pressure of less than 40 mmHg will not be entered into the study.

If a patient develops hypotension or experiences worsening hypotension during CRRT/SCD initiation (defined as a > 10 mmHg decrease in mean arterial pressure (MAP) during the first 15 minutes of CRRT initiation or integration of the SCD into the circuit), the patient, depending on the site PI's judgement, will receive a either a 10 ml/kg crystalloid bolus over 10 minutes or vasoactive medications will either have their dose increased (if already prescribed) or will be initiated. Each center will select the vasoactive medication that is best suited for the clinical indication.

6.2.3 SCD PLACEMENT IN CRRT / ECMO CIRCUIT

Appendix F illustrates the integration of the CRRT circuit and SCD into the ECMO circuit. The CRRT return will be post pump.

Patients who receive CRRT on ECMO almost always develop their AKI, and hence their need for CRRT, after they have been on ECMO for at least 24 hours. Thus, the additional extracorporeal volume (ECV) associated with the CRRT circuit is not a factor, as the blood volume from ECMO is stable. In fact, the contribution of the CRRT circuit is decreased (in terms of percent of ECV) since the ECMO circuit adds to the patient blood volume. The requirement for blood priming will be left to the clinical team treating the patient, as these cases will differ significantly from one another.

The pressure gradients are not an issue with CRRT on ECMO. In the most standard configurations, the CRRT circuit draws blood from the ECMO circuit post-pump and returns blood to the ECMO circuit pre-membrane, which is the safest configuration. The CRRT circuit will therefore see positive pressure from the ECMO circuit, and the current CRRT machines are designed to handle this. The CRRT pumps however, regulate the pressures within the CRRT circuit, so the SCD will see similar pressures compared to a non-ECMO situation.

6.2.4 Concomitant Medications

Since clearance or adsorption of medications have not been completely studied with SCD therapy, dosing of concomitant medications as per other extracorporeal therapies should be employed and evaluated during SCD treatment. In this regard:

- Subjects are permitted to take prescribed medications only.
- Continuously administered intravenous medications should be administered without interruption during SCD therapy
- Essential oral medications should be administered without adjustment of their dosing schedule
- Emergent intermittent intravenous and oral medications will be administered when required, without regard to the timing of SCD therapy
- For antibiotics, subjects will receive standard of care anti-infective dosing according to published schedules adjusted for CRRT [30]. Antibiotic serum levels will also be measured as per standard of care guidelines to ensure effective dosing and avoidance of toxicity.
- For vasopressors, dose adjustments will be made to achieve targeted mean arterial pressure.

A list of critical medications is listed in **Appendix C**. The clinical investigators will be alerted to evaluate dosing schedules for these medications carefully for potential adjustments to achieve desired effects during SCD therapy.

